 - g. Institutional Review Board membership list
 - h. Site personnel signature list
 - i. Financial Disclosure and Conflict of Interest forms for all site investigators
 - j. Patient screening and enrollment logs
 - k. Signed study Informed Consent Forms for each subject
 - l. Supporting source documentation for values and responses in case report forms
 - m. Supporting source documentation for adverse events

Informed Consent

The Informed Consent Form must be signed by the subject before enrollment into the study. A hardcopy of the Informed Consent Form must be provided to the subject. If applicable, informed consent should be obtained using Interpreter Services. If an interpreter is required to explain the study, the informed consent form will be reviewed with translation in the patient's native tongue, and a short consent document will be presented to the patient for signature in the language in which the patient is literate.

Signed Informed Consent Forms must remain in each subject's study file and be available for verification by the Study Sponsor at all times. Documentation of the date informed consent was obtained and a notation that a signed copy of the Informed Consent Form was provided to the study subject should be recorded. The informed consent process must always be conducted in a non-coercive manner.

Disclosure of Data

Subject data obtained for this study will be maintained as confidential, and disclosure to parties other than study personnel will be prohibited. Upon the study subject's permission, medical information may be given to his or her physician or other medical personnel for his or her welfare.

Retention of Records

Records and documents pertaining to the conduct of this study including case report forms, signed informed consent forms, protocol and amendments, supporting source documentation for values and responses in the case report forms, and supporting documentation for adverse events must be retained by the investigators for at least two years after conclusion of the study.

Feasibility

Brigham and Women's Hospital

Brigham and Women's Hospital (BWH) is a 793-bed acute tertiary care facility providing medical and surgical care for patients with general medical, cardiothoracic, orthopedic, oncologic, neurologic, obstetric, gynecologic, and gastrointestinal conditions. With the opening of the Heart and Vascular Center in 2014, BWH has solidified its position as a world leader in cardiovascular care and research, supporting an integrated care model in a single location. The Watkins Cardiovascular Clinic provides care to a large a growing outpatient population from the metropolitan Boston area, surrounding suburbs, and New England region. [name] cardiovascular medicine outpatient practice in the Watkin Cardiovascular Clinic, which is based in the Heart and Vascular Center, includes a large number of referrals for VTE and determination of the optimal duration of anticoagulation. The Watkin Cardiovascular Clinic also houses the outpatient practices of an additional seven Vascular Medicine faculty members and four Vascular Medicine fellows. These providers will serve as an important additional source of eligible study patients. The Vascular Medicine Section at BWH also staffs the Cardiovascular Medicine Consultation Service which evaluates and treats several hundred patients with VTE each year. The vast majority of these patients follow up in our outpatient clinics.

The BWH Thrombosis Research Group

The Thrombosis Research Group (TRG), directed by [name], Professor of Medicine, Harvard Medical School and Interim Chief of the Division of Cardiovascular Medicine and Section Head of Vascular Medicine, is based at BWH and Harvard Medical School. The Thrombosis Research Group has a decades-long commitment to VTE prevention and a dedication to improving the outcomes of all patients at risk for VTE. [name], Associate Professor of Medicine, Harvard Medical School, is the Associate Director of the Thrombosis Research Group and Assistant Section Head of Vascular Medicine at BWH as well as the Director of the Vascular Medicine Training Program. [name] is the Chair of the ACC PVD Section Leadership Council and serves on the Scientific Session Planning Committees for the AHA and SVM. [name] appreciates the national and global burden of recurrent VTE from his roles leading the Vascular Medicine educational initiatives for the ACC and AHA and from his perspective as a Co-Investigator on a number of VTE-related clinical trials (34–36) and observational studies (37). [name] is currently leading a clinical trial evaluating the safety and efficacy of apixaban for primary prevention of VTE in multiple myeloma patients on immunomodulatory regimens known to increase the risk of thrombosis (38). Drs. [name] and [name]'s dedication to and expertise in subject recruitment is clearly highlighted in their participation in the 7000-patient, multi-center, National Heart Lung and Blood Institute-sponsored Cardiovascular Inflammation Reduction Trial (CIRT) (39). Drs. [name] and [name]'s efforts have made BWH the top enrolling site for CIRT. [name] was the Principal Investigator of the ADOPT Trial of apixaban 2.5 mg twice daily for prevention of VTE in acutely ill medical patients during hospitalization and in the extended period after their discharge from the hospital (22).

The Thrombosis Research Group has an infrastructure of experienced leadership, with trained personnel in a multidisciplinary academic team (research pharmacists, cardiology fellows, research nurses, research coordinators, biostatisticians, administrators, and medical informatics specialists). Data storage and computing resources, as well as a network of regional, national, and international collaborating investigators, facilitate our execution of ongoing research projects and our planning of future research projects. The Thrombosis Research Group has studied all aspects of VTE, including epidemiology, diagnosis, treatment, and prevention. According to www.pubmed.gov, the group has authored more than 100 Original Reports since 2010.

Drs. [name] and [name] have extensive experience leading randomized controlled trials focused on prevention and treatment of thromboembolic disease. Examples of major Thrombosis Research Group-lead trials in this area include the 2500-patient multicenter Electronic Alert Trial (40), the 2500-patient multicenter Physician Alert Trial (41), the 2500-patient Discharge Alert Trial (42), and the 85-patient multicenter eTRIS trial (35).

Vascular Medicine at BWH is a regional Center of Excellence for VTE care. An EPIC Electronic Health Record query of the outpatient clinic volume of the five Vascular Medicine faculty providers and the 4 full-time Vascular Medicine fellows

demonstrated a provoked VTE volume of approximately 1500 new and follow-up patients.

Table 7. EPIC query estimate of new and follow-up provoked VTE patient volume in 2018.

Provider	Provoked VTE Volume (patients/year)
[name]	300
[name]	400
[name]	400
[name]	100
[name]	100
4 Full-Time Vascular Medicine Fellows	200
TOTAL	1500

Since running this EPIC analysis, we have also added two additional full-time Vascular Medicine faculty, [name] and [name]. Both specialize in the care of patients with VTE and see frequent referrals for determination of optimal duration of anticoagulation and long-term secondary prevention of recurrent events. Furthermore, we will recruit from our inpatient cardiovascular medicine consult service and cardiovascular medicine ward service which receive a high volume of provoked VTE referrals. Accordingly, we anticipate having the ability to draw on these additional sources of provoked VTE patients for at least another 100 provoked VTE patients per year.

Even without the added VTE patient volumes of [name] and [name], we calculate 1600 new and follow-up provoked VTE patients who present for outpatient visits at BWH per year and we conservatively estimate that 25% will fail to meet all the inclusion criteria or will meet at least one exclusion criterion. Therefore, an estimated 1200 patients will be eligible for enrollment in the trial in the first year.

We will also have our research nurse run reports from EPIC to identify other patients in our non-Vascular Medicine cardiology practices that will be eligible but may not be scheduled to see us. We will also aggressively communicate the launch of the study to our non-Vascular Medicine cardiology colleagues. Furthermore, we will recruit from our inpatient cardiovascular medicine consult service and cardiovascular medicine ward service which receive a high volume of provoked VTE. Accordingly, we anticipate having the ability to draw on these additional sources of provoked VTE patients for at least another 100 provoked VTE patients per year.

As the trial will enroll over 20 months, we estimate that we will be able to draw from 1200 patients in the first year and 800 patients in the 8 months that comprise the second year of enrollment. This will yield 2000 patients from which to enroll 600 subjects for the trial.

Based on our prior clinical trial experience at the BWH Thrombosis Research Group, we conservatively estimate that 50% of the patients who are screened and found to be eligible for the trial will consent to participate. Therefore, an estimated 1000 eligible patients would be willing to provide informed consent to participate in the HI-PRO trial. Accordingly, enrollment of the planned 600-patient study population should be feasible and efficiently accomplished at BWH.

Additionally, the BWH Thrombosis Research Group has the infrastructure to operationalize this enrollment plan. The Thrombosis Research Group has two full-time dedicated research assistants, a research intern, a research nurse, three faculty physicians, a full-time advanced Vascular Medicine fellow, and a number of general Cardiovascular Medicine fellows who participate in our research studies. We have coordinated our ongoing research projects to accommodate the percent efforts required by our research staff and physician team members to maximize our success at enrollment for this trial. Accordingly, we have adequate staffing and physician support to add to the research personnel for this trial, identify eligible patients, and maintain our enrollment on track. We also have an adequate reserve in staffing and flexibility to augment our effort should enrollment require it.

TRG led the patient recruitment effort for the Cardiovascular Inflammation Reduction Trial (CIRT), a randomized, double-blind trial of low-dose methotrexate in 4786 patients with previous myocardial infarction or multivessel coronary disease who additionally had either type 2 diabetes or the metabolic syndrome (39). CIRT was a landmark study which involved a novel application of a challenging anti-inflammatory drug, serial laboratory evaluations, and a high number of follow-up phone calls and in-person office visits, which required patients to travel from as far as California to Boston. Despite these challenges, TRG made BWH the overall top enrolling site in the CIRT trial.

We anticipate rapid enrollment in the HI-PRO trial. First, all the patients in the study will be familiar with anticoagulation and many will have received apixaban. Second, there are no study-mandated laboratory tests or office visits. Third, many patients with provoked VTE are reluctant to discontinue anticoagulation after the acute treatment phase because of the fear of recurrent events. We anticipate that many patients with provoked VTE will be highly interested in participating in a clinical trial of extended secondary prevention thromboprophylaxis, especially with the favorable safety and efficacy profile of low-intensity apixaban. It is quite possible that greater than 50% of eligible patients will want to participate and provide informed consent. In such a scenario, we would expect to enroll more quickly.

Potential Risks and Benefits

Potential benefits to the subject

The potential benefit of treatment with low-dose apixaban in patients with provoked VTE is secondary prevention of VTE, including fatal PE.

Potential Benefits to Society

The major potential benefit to society of the proposed trial of apixaban for secondary prevention of VTE in patients with provoked VTE is that if successful, the study will provide the foundation for a new indication for extended-duration anticoagulation for VTE prevention. The data acquired from this randomized, placebo-controlled trial will establish the safety and efficacy of low-dose apixaban versus placebo for extended prevention of recurrence after provoked VTE in patients with at least one persistent provoking factor. The study will draw widespread interest for apixaban in the extended prevention of recurrence after provoked VTE and will most certainly be of interest to high-impact peer-reviewed journals and to a broad spectrum of clinicians who will be better able to care for their VTE patients using these data.

Potential Risks to the Subject

The foreseeable risk of apixaban for secondary prevention of VTE in patients with provoked VTE is major bleeding.

Risks of Research Procedures Performed on Subjects

The risk of research procedures includes psychological discomfort from participating in a clinical trial (less likely) and loss of confidentiality of medical records or economic data (rare).

Women of childbearing potential (able to get pregnant) must have a negative pregnancy test before being considered for the study. It is not known how apixaban could affect an unborn child. Women of childbearing potential must use an effective method of birth control while participating in this research, as directed by their physician.

Anticipated Risks of Drug

Adverse reactions occurring in $\geq 1\%$ of patients treated for DVT and PE in the AMPLIFY study (source table 6 USPI)

- Epistaxis
- Contusion
- Hematuria
- Menorrhagia
- Hematoma
- Hemoptysis
- Rectal hemorrhage
- Gingival bleeding

Less common adverse reactions occurring in Eliquis-treated patients in AMPLIFY or AMPLIFY-EXT studies occurring with a frequency of $\geq 0.1\%$ to $< 1\%$:

- Blood and lymphatic system disorders: hemorrhagic anemia
- Gastrointestinal disorders: hematochezia, hemorrhoidal hemorrhage, gastrointestinal hemorrhage, hematemesis, melena, anal hemorrhage
- Injury, poisoning, and procedural complications: wound hemorrhage, postprocedural hemorrhage, traumatic hematoma, periorbital hematoma
- Musculoskeletal and connective tissue disorders: muscle hemorrhage
- Reproductive system and breast disorders: vaginal hemorrhage, metrorrhagia, menometrorrhagia, genital hemorrhage
- Vascular disorders: hemorrhage
- Skin and subcutaneous tissue disorders: ecchymosis, skin hemorrhage, petechiae
- Eye disorders: conjunctival hemorrhage, retinal hemorrhage, eye hemorrhage
- Investigations: blood urine present, occult blood positive, occult blood, red blood cells urine positive
- General disorders and administration-site conditions: injection-site hematoma, vessel puncture-site hematoma

Additional information about the risks of apixaban can be found in the Apixaban Med Guide (see Appendix).

Protection of Subjects against the Risks of Research Procedures

Before Study Enrollment

A rigorous screening process will be utilized to ensure that subjects with an increased risk of harm due to enrollment in the study are excluded from the study. This will include performing a detailed history and physical examination (to ensure that enrolled subjects truly fulfill all eligibility criteria) and carefully reviewing the results of laboratory testing (in particular, hematocrit, platelet count, INR, and serum creatinine).

During Follow-Up

Changes in health status during the 12-month follow-up period will be evaluated by the patient's primary physician, and other routine providers. All subjects enrolled will also have ongoing medical care with a dedicated Vascular Medicine provider. As apixaban is an FDA-approved drug commonly used for thromboprophylaxis and does not require routine follow-up clinical or laboratory monitoring for toxicity, the study will not mandate any follow-up visits or procedures other than those required for the patient's routine care.

Protection against Loss of Confidentiality

Subject confidentiality will be protected by maintaining all paper records in locked file cabinets in locked offices and all electronic records in password-protected computer files. All study data will be de-identified for storage in the electronic data repository. In addition, any identifying information will be removed from images or other data used in publication or presentations. All database information will be stored on computer systems that are located behind an electronic firewall, which will only permit access to certified study personnel. Access to study data files will be password-protected.

Use of Information and Publication

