- B. If the study is terminated or suspended, prompt notification will be provided to all parties of the study.
- C. Patient enrollment may be paused or terminated early if the DSMB determines that the potential benefits of continuing the trial are unlikely to outweigh the risks. For example, if the probability of achieving the target primary endpoints falls below a certain threshold, the trial will be stopped or paused for re-evaluation.

2. Safety Stopping Rules

The study will be terminated by the DSMB and principal investigator at any point if the following stopping criterion is met:

- a. An excess of morbidity or mortality is observed in patients receiving apixaban.
- b. When 3 of the subjects receiving apixaban experience an unprovoked intracranial hemorrhage, confirmed by independent adjudication and did not have a protocol violation such that he/she cannot be considered as representative of the intended patient population.
- c. When 3 of the subjects receiving apixaban experience an unprovoked major bleed (including fatal hemorrhagic events) and did not have a protocol violation such that he/she cannot be considered as representative of the intended patient population.

3. Stopping Rules for Futility

The study will be terminated by the DSMB and principal investigator if any of the following stopping criteria is met:

- a. Fewer than 36 events are observed in the placebo group at the time of the 300th patient interim statistical analysis
- b. Enrollment progress has been limited such that the study does not have a reasonable chance of randomizing 600 patients even after efforts to remediate recruitment

Protocol Violations

The study staff will rapidly and firmly address any protocol violations with the DSMB. If a protocol violation is detected or suspected, the investigator(s) will first be asked to provide a written explanation. After reviewing the available information, the study staff will categorize protocol violations as either major (eligibility or

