Baseline characteristics will be summarized by group. Any imbalances between the treatment groups for any demographic or baseline characteristic will be assessed based on clinical relevance in reviewing the summaries. For any differences deemed clinically relevant to the efficacy comparisons, exploratory analyses that include the imbalanced factor as a categorized covariate will be performed.

To account for the effect of baseline low-dose aspirin use in the study population on the rate of recurrent VTE after an initial provoked event, we will perform a pre-specified stratified efficacy analysis of patients receiving low-dose apixaban or placebo with low-dose aspirin compared with patients just receiving low-dose apixaban or placebo. We will calculate stratum-specific risk ratios (RR). Comparing the “crude” (overall or unadjusted) and stratum-specific risk ratios will enable us to determine whether aspirin modifies the effect of low-dose apixaban and to what extent. If the stratum-specific risk ratio is similar to the crude risk ratio, then there is minimal impact of low-dose aspirin. However, if the stratum-specific risk ratio differs from the unadjusted estimate by 10% or more, then low-dose aspirin modifies the effect of low-dose apixaban. We will conduct a similar analysis for the safety outcome of major bleeding.

We will also pre-specify subgroup analyses focused on the safety and efficacy of major populations of interest, in particular, elderly patients (age \geq 65 years), women, and those with persistent provoking factors of immobility, obesity, heart failure, chronic lung disease, chronic kidney disease, hemodialysis, chronic inflammatory/autoimmune disorder, and atherosclerotic cardiovascular disease.

Means, medians, and frequency distributions will be calculated for continuous variables. Number and percentages will be reported for binary and categorical variables. Differences between subgroups of interest will be examined using the chi-square or Fisher's exact test for binary and categorical variables and t-test or Wilcoxon Rank Sum for continuous variables (if the subgroups are of sufficient size for statistical comparison).

Safety outcome analyses will be performed among patients who received one or more doses of a study drug (Safety Population). All p-values reported will be two-sided. A p-value < 0.05 will be considered significant. All analyses will be performed using SAS software.

Interim Analysis

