The EINSTEIN CHOICE trial recently evaluated the safety and efficacy of regimens of full- or lower-intensity anticoagulant therapy versus low-dose aspirin for secondary prevention of VTE after an initial provoked or unprovoked event (2). The EINSTEIN CHOICE Investigators randomly assigned 3396 patients with VTE to receive either once-daily rivaroxaban (at doses of 20 mg or 10 mg) or 100 mg of aspirin. Prior to enrollment in EINSTEIN CHOICE, all study patients completed 6 to 12 months of anticoagulation therapy, and their providers were in equipoise regarding the need for extended anticoagulation. Approximately 60% of patients in EINSTEIN CHOICE had suffered provoked VTE. Symptomatic recurrent VTE occurred in 17 of 1107 patients (1.5%) receiving 20 mg of rivaroxaban and in 13 of 1127 patients (1.2%) receiving 10 mg of rivaroxaban, and in 50 of 1131 patients (4.4%) receiving low-dose aspirin (hazard ratio for 20 mg of rivaroxaban vs. aspirin, 0.34; 95% confidence interval [CI], 0.20 to 0.59; hazard ratio for 10 mg of rivaroxaban vs. aspirin, 0.26; 95% CI, 0.14 to 0.47; $P<0.001$ for both comparisons). Rates of major bleeding were similar (0.5% in the group receiving 20 mg of rivaroxaban, 0.4% in the group receiving 10 mg of rivaroxaban, and 0.3% in the low-dose aspirin group) (2).

Data from 4,553 patients in EINSTEIN CHOICE and the EINSTEIN VTE Continued Treatment Study demonstrate that provoked VTE patients with persistent provoking

factors have a reduction in recurrence with extended duration anticoagulation compared with low-dose aspirin or placebo (1.5% vs. 4.9%) (2,3). Common persistent provoking factors included immobility, obesity, heart failure, and chronic inflammatory disorders, such as Crohn's Disease and rheumatoid arthritis. Despite being highly prevalent, persistent provoking factors are rarely considered when stopping anticoagulation in patients with provoked VTE who have completed the typical 3- to 6-month duration of therapy. The 2016 American College of Chest Physicians (ACCP) Guidelines on Antithrombotic Therapy for VTE do not distinguish between transient and persistent provoking risk factors and recommend limited-duration anticoagulation for provoked events (4).

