- B. If the study is terminated or suspended, prompt notification will be provided to all parties of the study.
- C. Patient enrollment may be paused or terminated early if the DSMB determines that the potential benefits of continuing the trial are unlikely to outweigh the risks. For example, if the probability of achieving the target primary endpoints falls below a certain threshold, the trial will be stopped or paused for re-evaluation.

2. Safety Stopping Rules

The study will be terminated by the DSMB and principal investigator at any point if the following stopping criterion is met:

- a. An excess of morbidity or mortality is observed in patients receiving apixaban.
- b. When 3 of the subjects receiving apixaban experience an unprovoked intracranial hemorrhage, confirmed by independent adjudication and did not have a protocol violation such that he/she cannot be considered as representative of the intended patient population.
- c. When 3 of the subjects receiving apixaban experience an unprovoked major bleed (including fatal hemorrhagic events) and did not have a protocol violation such that he/she cannot be considered as representative of the intended patient population.

3. Stopping Rules for Futility

The study will be terminated by the DSMB and principal investigator if any of the following stopping criteria is met:

- a. Fewer than 36 events are observed in the placebo group at the time of the 300th patient interim statistical analysis
- b. Enrollment progress has been limited such that the study does not have a reasonable chance of randomizing 600 patients even after efforts to remediate recruitment

Protocol Violations

The study staff will rapidly and firmly address any protocol violations with the DSMB. If a protocol violation is detected or suspected, the investigator(s) will first be asked to provide a written explanation. After reviewing the available information, the study staff will categorize protocol violations as either major (eligibility or

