6.6 Interim Analysis

We will conduct a pre-specified interim analysis to assess the primary safety and efficacy outcomes after 50% of the planned enrollment population has completed 12-month follow-up. This planned interim analysis will inform the Data Safety Monitoring Board on whether the study should be stopped early due to efficacy, safety concerns, or futility or continue to enroll the full 600-patient cohort. The following three elements are used in considering the interim analysis:

6.7 Stopping for safety:

In the event that three distinct occurrences of unprovoked intracranial hemorrhages or major bleeding episodes are observed within the group of patients receiving apixaban, a thorough investigation will be conducted. This investigation will involve a review by an adjudication committee to confirm the authenticity of these incidents, ensuring that there have been no breaches of the study protocol that could have contributed to the adverse events. If the committee determines that these incidents are indeed linked to the apixaban treatment, specific measures will be implemented in response to these findings.

The decision to take action upon the confirmation of three such events is rooted in the clinical expertise of the researchers involved in the study. This threshold was established after extensive deliberation and consultation with the Mass General–Brigham Institutional Review Board (IRB).

The IRB is an independent body responsible for protecting the rights and welfare of human subjects involved in research, and their guidance plays a crucial role in maintaining the ethical standards of the study.

6.8 Stopping for futility:

The futility stopping rule is in place to prevent the unnecessary continuation of a clinical trial if there is a high likelihood that the primary efficacy outcome rate in the placebo arm falls below 6%. This threshold is considered clinically safe and is set to ensure that resources are not wasted on a trial that is unlikely to produce meaningful results. The problem is framed as a hypothesis testing scenario, where the null hypothesis states that the primary efficacy rate is greater than or equal to 0.06, and the alternative hypothesis suggests that it is less than 0.06.

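### The third apixaban major bleed terminates the study under the protocol but opens an investigation under the SAP, and neither document uses the placebo count

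*Combined protocol and SAP*

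**What the plan says.** The safety stopping rules read the same in the original and final protocol. Stopping Criteria, section 2, opens with "The study will be terminated by the DSMB and principal investigator at any point if the following stopping criterion is met". Three triggers follow.

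- Item a: "An excess of morbidity or mortality is observed in patients receiving apixaban". This is the only trigger worded as a comparison, and it has no metric or boundary.
- Item b: "When 3 of the subjects receiving apixaban experience an unprovoked intracranial hemorrhage, confirmed by independent adjudication".
- Item c: "When 3 of the subjects receiving apixaban experience an unprovoked major bleed (including fatal hemorrhagic events".

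Items b and c count only a patient who "did not have a protocol violation such that he/she cannot be considered as representative of the intended patient population". The word unprovoked is not defined for bleeding.

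SAP 6.7 begins "In the event that three distinct occurrences of unprovoked intracranial hemorrhages or major bleeding episodes are observed within the group of patients receiving apixaban" and then prescribes an investigation with committee review. If the committee links the events to apixaban, measures follow, but the SAP does not say what they are. It bases the threshold of three on clinical expertise and consultation with the IRB. Neither document gives the chance of reaching it.

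Two other protocol texts bear on this. The preface to the Stopping Criteria has the DSMB weigh efficacy as well as safety events before it recommends stopping. Interim Safety and Efficacy Analysis gives the DSMB the task of assessing event rates in both groups. Neither is made a condition of item c.

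**The concern.** A DSMB facing the third apixaban bleed would find termination in one document and an investigation in the other. In both, the trigger is an absolute count in one arm of a randomised placebo-controlled trial. The placebo rate does not enter, so the chance of reaching the count is the same whether placebo patients bleed less, equally or more.

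Hypothesis #2 is that major bleeding is similar in the two arms. If that is true, a mandatory stop can still end the trial for apparent harm and cut short the primary efficacy comparison. The SAP's attribution step does not replace a comparison, because the circumstances of a single bleed seldom show whether the drug caused it.

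**Working it through.** **Inputs.** 300 per arm, 1:1; VTE 6% on placebo and 1.5% on apixaban; two-sided alpha 0.05 (protocol, Sample Size Calculation). Major-bleed rates are 0.5% with rivaroxaban 20 mg and "0.4% in the group receiving 10 mg of rivaroxaban, and 0.3% in the low-dose aspirin group" (protocol, Introduction and Background). The 1% rate is my assumption.

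**1. The plan's own figure.** None exists for the bleeding rule. The sample size reproduces with the pooled-variance formula, mean proportion 0.0375:

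n = [1.96·√(2·0.0375·0.9625) + 0.8416·√(0.06·0.94 + 0.015·0.985)]² / 0.045² = 278.6, so 279 per group, with power 0.8005 as stated. At 300 per group the same formula gives 0.828.

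**2. Chance of three or more apixaban bleeds.** X ~ Binomial(300, r), P(X ≥ 3) = 1 − P(0) − P(1) − P(2). At r = 0.4%: 1 − (0.300 + 0.362 + 0.217) = 0.120. The half-count column uses r/2, as if half of major bleeds counted as unprovoked.

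| Rate r | Expected bleeds | All bleeds count | Half count |
|---|---|---|---|
| 0.3% | 0.9 | 6.3% | 1.1% |
| 0.4% | 1.2 | 12.0% | 2.3% |
| 0.5% | 1.5 | 19.1% | 4.0% |
| 1.0% (assumed) | 3.0 | 57.8% | 19.1% |

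These hold for any placebo rate, including one equal to r.

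**3. Placebo count when the rule is met, equal rates.** Let P be the chance that one arm reaches three bleeds. Both arms reach three with probability P², and by symmetry placebo gets there first in half of those trials. Given that apixaban reaches three, placebo already has three or more with probability (P²/2)/P = P/2. This gives 3.1%, 6.0% and 9.5% at 0.3%, 0.4% and 0.5%, and 28.9% at 1%. If placebo bleeds twice as often (0.8% against 0.4%), the trigger chance is still 12.0%, and placebo already has three or more in 24.7% of triggers.

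**4. Effect on the efficacy analysis if termination is mandatory.** Simulated log-rank test, 8,000 trials per rate: 300 per arm, uniform accrual over 20 months, 12 months of follow-up, exponential VTE times, no dropout, every bleed countable, data cut at the third apixaban bleed. Power is about 86% without the rule, 84% at 0.4%, 82% at 0.5% and 71–72% at 1%. The 86% exceeds the 0.828 in step 1 because the test and the approximation differ.

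**5. Evidence in the smallest split.** Under equal risk, three apixaban and no placebo bleeds has one-sided exact p = 0.5³ = 0.125.

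**6. Items b and c.** The protocol's major-bleed definition includes bleeding in a critical site, so an intracranial hemorrhage will ordinarily count under item c as well. Item b requires independent adjudication in its own wording; item c does not. SAP 6.7 merges the two and sends both to adjudication.

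**The case against.** The strongest case for the rule is that it is a protective cap and was not meant as a comparative test. The SAP records deliberation and IRB consultation behind the number three, and guidelines quoted in the protocol would stop anticoagulation at three months in many of these patients. An absolute ceiling on serious bleeds is a defensible precaution. That stands, and it argues against demanding a statistical excess before any stop: by step 5, a conventional boundary would not act even on a 3–0 split. The efficacy cost is also modest at the cited rates, with power staying above the planned 80%.

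Four stronger readings are tempting, and the documents do not support them.

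- *The rule ends the trial.* That is true of the protocol sentence only. SAP 6.7 investigates first, and the protocol's own preface has the DSMB weigh efficacy events.
- *It usually fires when placebo bleeds as often.* With unlimited follow-up, placebo would have three or more bleeds half the time when apixaban reaches its third. With 300 per arm followed for 12 months, this happens in about 3–10% of triggers at the cited rates.
- *Item b can never act alone.* The definition does not list its critical sites, and the case report form offers an intracranial location under clinically relevant non-major bleeding too. The overlap is large but not proved complete.
- *Leaving out protocol violators contradicts the Safety Population.* The protocol says "Safety outcome analyses will be performed among patients who received one or more doses of a study drug (Safety Population", which defines an analysis set. A monitoring rule may count differently.

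**Conclusion.** The concern holds in this form: the protocol and SAP attach different consequences to the third apixaban bleed, neither uses the placebo count, and the chance of reaching the threshold is not reported. With no true excess, the count is reached in about 6–19% of full trials at the cited 0.3–0.5%. The main problem is therefore triggering when the arms do not differ; stopping while placebo bleeds as much or more is possible but uncommon.

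The size rests on three assumptions: rates borrowed from another drug's trial, all 300 apixaban patients followed for 12 months, and every major bleed countable. Halving the countable bleeds brings the range to about 1–4%; a 1% rate raises the full-count figure to 58%. The loss of power applies only if the protocol's termination wording is followed literally. This should be corrected, because it leaves a live decision rule ambiguous, but it does not invalidate the design.

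**What to change.** 1. Reconcile protocol Stopping Criteria section 2 with SAP 6.7 on what the third apixaban event does, and say what the SAP's measures are.
2. State in both that the review at that event includes CEC-adjudicated major-bleed counts in both arms.
3. Report the rule's operating characteristics over a range of bleed rates, with a definition of unprovoked.
4. Reconcile items b and c on overlap and on adjudication.

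Whether to set a termination boundary, and where, is for the DSMB and IRB; the protocol already has the DSMB establish stopping rules at its kick-off meeting.

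The cost is wording in the protocol, SAP and DSMB charter. No new data are needed, since the DSMB already has the task of assessing event rates in both groups. One downside should be stated openly: if the protocol is aligned to the SAP, a cluster of apixaban bleeds leads to a review and not to an automatic stop.
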